1. INTRODUCTION

1.1. Background and rationale

Background

The US government has made the historic declaration of the current opioid crisis as a public health emergency. And though this action will allow for expanded access to telemedicine services and reallocate funding for abuse programming, it remains the responsibility of researchers to propose clinical solutions that can improve patient outcomes. From 2014 to 2015 the death rate from synthetic opioids, such as fentanyl, increased by 72.2%. While all of Illinois was distinguished among other states with a significant increase in drug overdose death rates from 2013-2015 by the Center for Disease Control (CDC) and Illinois Department of Public Health (IDPH), people living in rural communities are more likely to overdose on prescription pain medications than people in cities. This poses an obstacle for all clinicians, and particularly those charged with pain management following surgery. Thoracic surgery requiring thoracotomy is widely recognized as one of the most painful surgical procedures, and is associated with extended hospital length of stay, respiratory morbidity, and delayed post-surgical return of function. Intercostal nerve damage and muscular trauma are considered the principal causes of postoperative pain after thoracotomy. Medical management of postoperative pain utilizing opioids and NSAIDs has become the standard approach for post thoracotomy analgesia; whereby de minimis opioid use is a requirement for patient discharge conversely contributing to increased hospital length of stay.

Over the last 3 decades clinicians have levied increasing emphasis on minimally invasive surgical techniques, reducing the risk of intraoperative complications in surgery by demonstrably reliable improvements in postoperative outcomes. Video-assisted thoracoscopic surgery (VATS) is a minimally invasive technique which eliminates the necessity of rib retraction and shrinks the incision size, reducing intercostal nerve and muscular trauma to preserved pulmonary function. This methods relies on visualization of the mediastinal anatomy and surgical apparatus using a camera. Further advancement over the last decade has broadened the indications for VATS utilization to encompass more complex procedures, marginalizing the need for open thoracotomy practices.

Though VATS shows comparable benefits to open thoracotomy being a safer alternative for elderly patients, low postoperative pulmonary complications, decreased trauma, no rib spreading, lower hospitalization, and a faster recovery, patients still risk moderately severe acute postoperative pain. Successful management of postoperative pain after VATS is indicative of adequate post-surgical recovery as suboptimal postoperative pain management may lead to chronic pain, which may be or become neuropathic in nature. Thoracotomy is suspected to induce chronic pain at 57% percent of patients surviving a year after surgery, where pain was severe in 8% of those cases. 30-50% of patients were shown by one study to have postoperative pain at the thoracotomy site after 2 months which can be credited by a considerable amount to intercostal nerve injury with a neuropathic origin. And though some patients in this study found post-thoracotomy pain

after 1-year, some of those same patients did not report any pain symptoms at 6 months. Long term follow-ups for pain management after thoracotomy are not standard care per common practices. Additionally, though there is a treasure trove of evidence connecting VATS to chronic pain, very little has been done to conclusively detail the relationship between post-thoracoscopy chronic pain and opioid dependence which may arrive later in a patients' medical history. The gravity of the transpiring American public health emergency has inspired the research community to ardently consider this issue. Minimally invasive procedures like VATS are incomplete solutions to post-operative pain management where chronic pain and drug dependence require greater consideration.

Increasing utilization of non-opioid medications as surrogate opioid management for post-thoracotomy pain could potentially diminish the medical reliance on and incipient patient risks incurred as a result of opioid use for VATS procedures. Comparisons of different analgesic methods reveal reduced incidence and intensity of long-term procedural pain. Bupivacaine HCl, marketed under the names Marcaine, Sensorcaine, and Vivacaine-- is the current non-opioid drug of choice for thoracic epidural analgesia in 89.7 percent of surgical cases. Marcaine behaves as the amino-amide anesthetic *1-butyl-N-(2, 6-dimethylphenyl) piperidine-2-carboxamide* achieving moderate inhibition of Na (+) ion transduction across the neuronal membrane by decreasing the membrane permeability and consequently inhibiting the excitation of neurons to depress the pain response. Amino-amide anesthetics are commonly associated with hypotension and can enhance the hypotensive effects of a number of antihypertensive drugs. Other adverse reactions like cardiac arrest, bradycardia, apnea, and hypoventilation have also been associated with Amino-amide local anesthetics. Marcaine is approved for localized analgesia and regional blocking by the Food and Drug Administration under Hospira, Inc. and has since received wide recognition in thoracic surgery for postoperative pain management following thoracotomy. Contrarily, Marcaine reports only a duration of action of < 6 hours per dose administration. Continuous local administration of bupivacaine has been shown to reduce pain, cytokine levels, and opioid requirements postoperatively. This limitation pressures anesthesiologist, surgeons, and nursing staff through inordinate surveillance of a consistent need for analgesia to coordinate additional measures for pain management such as the administration of NSAIDS and narcotics. Ancillary support of bupivacaine HCl infusion utilizing epinephrine and/or perineural catheters come short of remediation to the limited duration of action. The potential to increase the duration of adequate local analgesia by other novel means may have an effect on dosing requirements, and offer a way to reduce the blood concentration of bupivacaine. A 2015 study by the University of Texas Medical School of 85 participants undergoing open thoracotomy comparing the use of the liposomal bupivacaine formulation known as Exparel as an intercostal nerve block to their current thoracic epidural standard resulted in significant pain control postoperatively.

The liposomal version of bupivacaine marketed by Pacira Pharmaceuticals in 2011, is indicated for single-dose post-surgical administration into surgical site to produce local analgesia. Vesicular encapsulation has been confirmed as a novel method of extending

delivery of anesthesia and, as a multi-vesicle liposome formulation of bupivacaine, Exparel provides an extended duration of action reporting > 72 hours of post injection analgesia. Liposomes are loaded with bupivacaine by an ammonium sulfate gradient established at an appropriate pH for complete saturation of the vesicles with bupivacaine. The drug is released gradually after dispensation to provide steady analgesia to the affected area. Exparel was initially approved by the FDA for treatment of patients undergoing bunionectomies or hemorrhoidectomies. The FDA has since broadened the indication of Exparel to “administration into surgical site to produce postsurgical analgesia.”

While assessing whether use of a higher fidelity analgesia will affect the requirement for narcotic administration for postoperative pain and the risk of opioid dependence and abuse observed when postoperative pain is treated with a longer, steady release of anesthesia over time, this study aims to consider outcomes related to patient hospital costs as well as short and long term pain assessment after hospital discharge.

Hospital costs associated with VATS anesthesia narcotic use in rural Illinois community has not been subjected to the due scrutiny necessary to understand the effect of the opioid crisis; the Council of Economic Advisors report on this insurgence estimates the overall national cost in 2015 at nearly \$504.0 billion and climbing. IDPH semiannual report on opioid trends in hospitalizations and emergency department visits show continued increase annually since the 2016 and an overall upward trend since 2013. A report by SIU School of Medicine places estimated direct medical costs in 2009 at \$2.2 billion. Ad caveat-- these estimates includes long term data collected on downstream effects of opioid abuse, which has been unfortunately and indelibly correlated to prescriptions for anesthesia during surgery, including the rise in healthcare resources utilized over time by opioid abusers as compared to their non-addicted peers, costs to the criminal justice system, and fatality costs of lost potential earnings. This study does not intend to assess the impact on other downstream economic factors, though by collecting comparison data on healthcare charges as a result of narcotic requirements from use of local administration of Exparel and Marcaine for VATS, the preferred surgical technique for lung diseases by SIU Medicine Cardiothoracic surgeons, we can increase our understanding of the disparity that opioid crisis plagues on the bottom line of our hospital and the pockets of its patrons. Though both of these drugs provide a non-opioid analgesic and are available and indicated for the intended use, the gross differences in their durations of activity underscore a potentially significant difference in the necessity of narcotic use for post-thoracotomy pain which we plan to further describe in the proposed research. To be able to efficaciously distinguish between the two drugs is in the best interest of our patients.

Currently, there is very little published data representing these outcomes in consort. Growing preference for local analgesia and intercostal nerve blocking with Exparel for pain after thoracotomy presents a unique opportunity to study the effects on cost, length of hospital stay, and primarily the comparative downstream effect on narcotic

requirements pain management. Per our own query, 1 clinical trial currently registered with clinicaltrials.gov compares Exparel and Marcaine prospectively for post-operative pain management following lung surgery. No other study currently intends to analyze chronic neuropathic pain, opioid usage, and hospital cost data. In our current clinical setting, the use of Marcaine versus Exparel is based purely on physician preference.

2. STUDY OBJECTIVES

The hypothesis is the possibility of liposomal bupivacaine providing more relief with less need of narcotics when compared to standard bupivacaine. To compare pain management following local infiltration of liposomal bupivacaine (Exparel®) versus standard bupivacaine HCl with epinephrine (Marcaine®) after VATS (video-assisted thoracoscopic surgery)-lobectomy. This will be accomplished by evaluating total opioid usage and patient reported pain scores.

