2.1. Efficacy Outcomes Measured

2.1.1. *Primary Outcomes*

- i. Total morphine equivalents consumed during 72 hours post-op

2.1.2. *Secondary Outcomes*

- i. Patient self-reported pain visual analog scale score
- ii. Narcotic or pain medications consumed throughout hospitalization and during first 30 days, 6 months and 1 year post-lobectomy
- iii. Incidence of Paresthesia
- iv. Time until first opioid usage
- v. Anti-emetic usage
- vi. Length of hospital stay
- vii. Postoperative complications (e.g. pneumonia, pulmonary complications, wound infections etc.)
- viii. Time to ambulation
- ix. Time to first bowel movement
- x. Time to chest tube removal
- xi. Peak expiratory flow measurements
- xii. Intraoperative versus postoperative pain management costs
- xiii. Overall Hospital Cost

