5. STATISTICAL METHODS AND DETERMINATION OF SAMPLE SIZE

Based on the results of the Parascondola et al study, a power analysis was performed to determine the necessary sample size in the 2 treatment arms for the proposed study. While the Parascondola study only examined inpatient narcotic use for the first 72 hours post-op, we plan to include all narcotic usage in this time period as the primary outcome of the proposed study. The estimated difference between the groups at 72 hours produced an effect size of $d=0.862$. This effect size would only require a sample size of 31 in each group to achieve a power of .90 to detect a statistically significant difference for $\alpha=0.05$. Given the attrition in the Parascondola study, it would seem advisable to view this effect size as having a certain degree of unreliability associated with it. Therefore, we also examined the magnitude of the difference in treatment groups which was observed at the 60 hour time point ($d=0.503$). Using the mid-point of $d=0.6825$, 49 subjects per group would be required to have statistical power=0.90 for $\alpha=0.05$. Even if the underlying effect size were $d=0.5$, a sample size of 75 per group would have power=0.84 with $\alpha=0.05$. This sample size ($n=75/\text{group}$) should also provide reasonable power to detect significant differences for the secondary outcomes of pain assessment at 24, 48 and 72 hours, as well as the cumulative pain score at 72 hours (area under the curve - AUC_{72}). Sample size determination was made using G*Power 3.1.9.2. (Faul, F., Erdfelder, E., Buchner, A., & Lang, A.-G. (2009). Statistical power analyses using G*Power 3.1: Tests for correlation and regression analyses. Behavior Research Methods, 41, 1149-1160.)

Statistical Methods

Descriptive statistics including means (standard deviations), medians (interquartile ranges – IQRs) and frequencies (counts / percentages) will be used to present the baseline characteristics for the 2 groups. Independent group's t-tests, Wilcoxon rank-

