sum tests and chi-squared tests of independence (or exact tests as appropriate) will be used to compare baseline characteristics of the 2 groups to assess effectiveness of randomization. Wilcoxon rank-sum tests will also be used to test for differences between the groups on the primary outcome measure, cumulative narcotic use over the first 72 hours post-op, as well as secondary outcomes including pain scores, length of stay and cost. Chi-squared tests, or Fisher's exact tests will be used to compare the proportions of patients in the 2 groups experiencing complications or using opioids at 6 and 12 months.

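### The hypothesis pairs better pain relief with lower opioid use, but the relief half has no single, error-controlled test and no rule for reading it beside the opioid result

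*Combined protocol and SAP*

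**What the plan says.** Section 2 gives a hypothesis with two parts: "The hypothesis is the possibility of liposomal bupivacaine providing more relief with less need of narcotics when compared to standard bupivacaine". On how the objective will be met, it adds: "This will be accomplished by evaluating total opioid usage and patient reported pain scores".

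Section 2.1.1 lists one primary outcome: "Total morphine equivalents consumed during 72 hours post-op". Section 2.1.2 lists thirteen secondary outcomes, the first being "Patient self-reported pain visual analog scale score", with no time point attached.

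Section 5 bases the sample size on opioid use. It then says that 75 per group should give reasonable power for pain at 24, 48 and 72 hours and for AUC72, without giving a pain effect size or SD. Under Statistical Methods, "Wilcoxon rank-sum tests will also be used to test for differences between the groups on the primary outcome measure, cumulative narcotic use" over 72 hours, and the same test serves "secondary outcomes including pain scores, length of stay and cost". AUC72 is not named there or in Section 2.1.2.

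Section 4.1 describes efficacy differently: the percentage of subjects with at least one component of a major morbidity, the listed components being morphine-equivalent dose and VAS pain. It sets no thresholds, and Section 5 does not analyse this variable.

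The first footnote to Table 1 leaves pain assessment from postoperative day 1 until discharge to standard of care.

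**The concern.** Opioid dose and pain score are two views of one response. A patient given less opioid may hurt more, while a patient dosed to comfort may show no pain difference at all. A fall in morphine equivalents therefore supports the opioid half of the hypothesis but cannot by itself show better relief. The relief half has to come from the pain data.

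For those data the plan offers four analyses and does not say which one counts, in what order they are tested, or how they are read beside the primary result. Two things are at stake. A favourable pain p-value could be picked after the fact to complete the two-part claim. And if opioid use falls while pain does not differ, nothing written in advance says what the report may conclude.

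**Working it through.** **1. The plan's own figures.** Inputs from Section 5: d = 0.862 at 72 hours, d = 0.503 at 60 hours, mid-point (0.862 + 0.503)/2 = 0.6825, alpha 0.05 (sides not stated). Two-sided Wilcoxon power from the noncentral t, with effective n = n × 3/π:

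- d = 0.862, power 0.90: 31 per group (stated 31).
- d = 0.6825, power 0.90: 49 per group (stated 49).
- d = 0.5, n = 75: effective n = 75 × 3/π = 71.6; noncentrality 0.5 × √(71.6/2) = 2.99; power 0.844 (stated 0.84).

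The figures reproduce under a two-sided test. All of them concern opioid use; none concerns pain.

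**2. The two halves side by side.**

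| | Opioid use | Pain relief |
|---|---|---|
| In the hypothesis (Section 2) | yes | yes |
| Rank (Section 2.1) | sole primary | secondary |
| Analyses named (Section 5) | one | four, unranked |
| Effect size for power | given | none |
| Order or key measure | not needed | none |

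The Section 4.1 variable does not fill the gap. It has no thresholds and no analysis, and a rule met by either component would not require a benefit on both.

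**3. Picking one favourable result from four.** The harm is a false result in favour of liposomal bupivacaine, so the relevant rate for one two-sided 0.05 test is 0.025.

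- Four independent tests: 1 − 0.975⁴ = 0.096.
- Correlated tests: three standard normal statistics with common correlation ρ, AUC72 taken as their standardised mean, and the chance that the largest of the four exceeds 1.96. Simulation gives about 7% at ρ = 0.3 and about 5.5% at ρ = 0.7.

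The documents give no correlation; 0.3 to 0.7 is assumed. AUC72 summarises the same scores, so full independence cannot hold and 9.6% is a ceiling.

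**4. Power of the two-part claim.** Assumptions: 75 per group, opioid d = 0.5, each test at two-sided 0.05, bivariate normal statistics with correlation 0 to 0.5, and assumed pain effects. The opioid test alone has power 0.849 on this normal approximation. At zero correlation the joint power is the product of the two powers; at pain d = 0.5, for example, 0.849 × 0.849 = 0.721.

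| Assumed pain effect (SD) | Joint power |
|---|---|
| 0.3 | 0.37 to 0.41 |
| 0.4 | 0.57 to 0.62 |
| 0.5 | 0.72 to 0.76 |

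**5. How often the mixed result arises.** With opioid d = 0.5, truly equal pain, and an assumed correlation of −0.3 to 0.3, the chance of a significant opioid result with observed pain no better is 0.40 to 0.45. That is about half of the 0.849, so the wording for this case should be settled in advance.

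**The case against.** The choice of primary outcome is defensible. The closing part of Section 1.1 makes the effect on narcotic requirements the main interest, and one opioid primary with pain as a secondary is a coherent design. Pain is not neglected: it is listed first among the secondaries, has a named test and is considered in the sample-size text. All of this stands, and the primary outcome should stay as it is.

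Four stronger readings are tempting, and the documents do not support them.

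- *The trial will declare success on opioid amount alone.* No success rule is written, and Section 2 says that both opioid use and pain scores will be evaluated. The defect is the missing rule.
- *Fewer opioids at equal pain contradicts the hypothesis.* It does not: with opioid given to comfort, that is what a better local anaesthetic could produce. It leaves better relief unshown. Worse pain would be a different matter.
- *The error rate is 19%.* 1 − 0.95⁴ = 0.185 counts false results in both directions under independence. Only the favourable direction matters here.
- *All thirteen secondaries are tested separately.* Section 5 names tests for only some of them; paresthesia, time to ambulation and peak flow, for example, have none.

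It is also fair to say that AUC72 is not yet fit to be a key outcome, since no assessment times are fixed. The fix has to cover that.

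**Conclusion.** The concern holds as a gap in the link between hypothesis and analysis. The primary test, its alpha and the stated sample size are sound for opioid use. The relief half of the hypothesis has no single error-controlled test, and no rule says what each combination of opioid and pain results would support.

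The selection risk is modest: about two to three times the 2.5% of a single test at the assumed correlations (5.5/2.5 = 2.2; 7/2.5 = 2.8), and at most 9.6%. These figures assume two-sided 0.05 for each pain test, which the plan does not state. The power range for the two-part claim rests on assumed pain effects, because the documents give none. Closing the gap is a cheap improvement; leaving it open would not invalidate the primary analysis.

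**What to change.** In Sections 2 and 5, before any unblinded analysis:

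1. Keep the 72-hour morphine-equivalent comparison as primary at 0.05.
2. Only if it is significant in favour of liposomal bupivacaine, test AUC72 pain at 0.05 as the single key pain outcome. Treat pain at 24, 48 and 72 hours as descriptive. The fixed order needs no split of alpha.
3. Make the two-part claim only if both tests are significant in favour of liposomal bupivacaine. If only the opioid test is, conclude opioid-sparing and report the AUC72 difference with its 95% CI beside it.
4. Do not add a rule that withdraws the opioid-sparing conclusion whenever the observed pain difference points the other way. With truly equal pain and the assumptions in step 5 of the working, it would cut the chance of that conclusion from about 0.85 to between 0.849 − 0.452 = 0.40 and 0.849 − 0.397 = 0.45.
5. Add AUC72 to Section 2.1.2, with fixed assessment times and a rule for patients discharged before 72 hours, and align Table 1.
6. Reconcile the Section 4.1 efficacy variable with Section 2.1.1, or remove it.

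The cost is a few sentences plus scheduled pain assessments in place of standard-of-care timing. The primary test, alpha and sample size do not change. Two downsides should be stated in the plan: the two-part claim has less power than 0.84 (about 0.37 to 0.76 for an assumed pain effect of 0.3 to 0.5 SD), and no formal relief claim is possible if the opioid test is negative.

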2.1. Efficacy Outcomes Measured

2.1.1. *Primary Outcomes*

- i. Total morphine equivalents consumed during 72 hours post-op

2.1.2. *Secondary Outcomes*

- i. Patient self-reported pain visual analog scale score
- ii. Narcotic or pain medications consumed throughout hospitalization and during first 30 days, 6 months and 1 year post-lobectomy
- iii. Incidence of Paresthesia
- iv. Time until first opioid usage
- v. Anti-emetic usage
- vi. Length of hospital stay
- vii. Postoperative complications (e.g. pneumonia, pulmonary complications, wound infections etc.)
- viii. Time to ambulation
- ix. Time to first bowel movement
- x. Time to chest tube removal
- xi. Peak expiratory flow measurements
- xii. Intraoperative versus postoperative pain management costs
- xiii. Overall Hospital Cost

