3.4. Study procedures

3.4.1. Summary

All patients scheduled for surgical consult with Cardiothoracic Surgery for possible VATS lobectomy will be prescreened for initial eligibility criteria. Subjects who elect to go forward with surgery will be presented with the opportunity to participate in the study. Informed consent form will be discussed in detail at the clinic or MMC (for in-patient potential subjects) by authorized study personnel. Patient will be given time to review the informed consent with family if so desired. After the patient voluntarily agrees to participate (sign ICF), their inclusion/exclusion criteria will be reviewed again

based on SOC testing to ensure continued eligibility. Patient data such as vitals, physical examination (PE), medications, and medical and surgical history will be recorded or obtained from the EHR. Subjects will be randomized to one of two groups, test (A) and active control (B), Night or morning of scheduled surgery. At the end of surgery, study drug will be administered as described in details below per the standard FDA guidelines. Outcomes will be measured during post-operative hospital stay and until 1 year after surgery for extended follow up which is the standard protocol with CT surgery. A schedule for all assessments throughout the study is described in table 1 at the end of this document.

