3.4.5. Assessment periods and associated observations and measurements

Described in schedule of assessments in Table 1

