7. ASSESSEMENT OF SAFETY

Stopping rules and attributes of seriousness, unexpectedness, severity and causality will be assigned by the investigators and further reviewed during monthly meetings, or as needed based on urgency, as part of the data and safety monitoring plan (DSMP).

Summary: Screening eligibility will be reviewed based on standard of care testing done for the elective index procedure. Adverse events (AE) will be monitored and recorded daily throughout the subjects' hospital stay and again at their post-surgical follow-up visits (30 day) and at 6 month and 1 year (part of standard of care) either in person or through review of subjects' EHRs and phone interviews. These will be reviewed individually by the PI and co-investigators and reported by study personnel. An adverse event log will be created for this study. Regularly scheduled meetings of study personnel will take place to review study progress, procedures, AEs and safety considerations. Real time management of AEs will be done per standard of care by the subjects' health care providers. Any serious AE or unanticipated problems will be reported to the Springfield

Committee for Research Involving Human Subjects (SCRIHS) in accordance with SCRIHS policy.

Specification of Safety Parameters: Safety of exparel and marcaine will be evaluated in this study. Safety endpoints will include:

- (1) Adverse events including serious adverse events (SAEs), suspected ADRs, and discontinuations due to AEs
- (2) Physical examination
- (3) Vital signs

Table 1: Schedule of study assessments

Assessment	Baseline/ Screening	Pre-op (D0)	OP (D0)	Each POD	hospital discharge	F/UP (D30 ± 7d)	F/UP (6m)	F/UP (12m)
Inclusion/exclusion	X	X						
ICF	X							
Vitals	X		X	X	X	X	X	X
PE (done as standard of care by any authorized clinical team member)	X		X	X	X	X	X	X
Medical/Surgical History	X							
Concomitant medications (excluding pain Rx)	X	X	X	X	X	X	X	X
Pain/opioid medication log	X	X	X	X	X	X	X	X
Randomization		X						
Study drug administration			X					
Pain-VAS	X		X	X*	X*	X	X	X
Incentive spirometry (done at bedside)			X	X	X			
MEQ**			X	X	X	X	X	X
Complications			X	X	X	X	X	X

*On POD1 and later, pain assessment will be done as is standard of care by hospital staff until discharge.

** Calculation of MEQ using <http://clinicalcalc.com/Opioids/>

References:

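### Table 1 schedules no specific assessment of two listed secondary outcomes, paresthesia and peak expiratory flow, and neither is defined elsewhere in the supplied text

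*Combined protocol and SAP*

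**What the plan says.** Section 2.1.2 of the combined protocol and SAP lists 13 secondary outcomes. Item iii is "Incidence of Paresthesia" and item xi is "Peak expiratory flow measurements". Neither comes with a definition, instrument or time point.

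Section 3.4.1 states: "A schedule for all assessments throughout the study is described in table 1 at the end of this document". Section 3.4.5, where observations and measurements would be set out, contains only a pointer: "Described in schedule of assessments in Table 1".

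Table 1 has 13 rows. The ones closest to these outcomes are:

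- **Physical examination**, at screening and from the operation through 12 months, described as "PE (done as standard of care by any authorized clinical team member").
- **Complications**, from the operation through 12 months.
- **Respiratory measurement**, a single row: "Incentive spirometry (done at bedside"). It is marked for the operation, each postoperative day and discharge only.

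Outside Table 1, Section 7 says "Adverse events (AE) will be monitored and recorded daily throughout" the hospital stay, and again at 30 days, 6 months and 1 year. Section 3.4.4 blinds the subjects and the study statisticians but not the surgical team or the coordinators. Section 6 makes the coordinators responsible for data collection, on appendix 1 forms that are not in the supplied text.

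**The concern.** A symptom that nobody asks about, or a flow that nobody measures, cannot be recovered at analysis.

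For paresthesia, the result would be an incidence of what was noticed and written down. That is likely to fall below the true incidence, which costs power. The staff who examine patients and collect data know the allocation, so recording could also differ between arms and create a difference where there is none. Section 1.1 attributes lasting pain after thoracotomy in considerable part to intercostal nerve injury. It also names neuropathic pain as one of three elements of the trial's novelty: "No other study currently intends to analyze chronic neuropathic pain, opioid usage, and hospital cost data". Paresthesia is the only listed outcome specific to nerve symptoms, since a VAS records intensity and not character.

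For peak expiratory flow, the measurement in Table 1 is of another kind. Incentive spirometry is an inspiratory-volume manoeuvre and does not itself yield an expiratory flow.

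**Working it through.** **1. Outcomes against the schedule**

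| | Paresthesia (iii) | Peak expiratory flow (xi) |
|---|---|---|
| Table 1 rows naming it | 0 of 13 | 0 of 13 |
| Nearest route | Physical examination, complications; adverse events (Section 7) | Incentive spirometry |
| Does that route specify it? | No: no sensory content in the examination row; not in the Section 4.3 list; not named in Section 7 | No: different measurement |
| Timing of that route | In hospital, day 30, 6 and 12 months | Operation day to discharge; no baseline |
| Named in the Section 5 analysis | No | No |

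Time to ambulation, first bowel movement, chest tube removal, length of stay and costs also lack a row, but these can plausibly be taken from the chart or billing record. A symptom at 6 or 12 months cannot be relied on to appear there, particularly as Section 7 allows those contacts to be made by record review and telephone.

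**2. Illustration of the size for paresthesia**

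The plan gives no paresthesia rate and no power for this outcome, so there is no stated figure to reproduce. The 75 evaluable subjects per arm come from Sections 3.3 and 5. All rates and capture fractions below are assumptions.

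For a two-sided 0.05 comparison of two proportions with n = 75 per arm:

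- s0 = √[2p̄(1−p̄)/n], where p̄ is the mean of p1 and p2
- s1 = √{[p1(1−p1)+p2(1−p2)]/n}
- rejection probability = Φ[(|p1−p2| − 1.96·s0)/s1] + Φ[(−|p1−p2| − 1.96·s0)/s1]

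*Loss of power.* True rates are assumed to be 40% v 20%.

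- Full capture, 0.40 v 0.20: s0 = 0.0748, s1 = 0.0730. (0.20 − 0.1467)/0.0730 = 0.73, so power = 0.77.
- Half captured in both arms, 0.40 × 0.5 = 0.20 v 0.20 × 0.5 = 0.10: s0 = 0.0583, s1 = 0.0577. (0.10 − 0.1143)/0.0577 = −0.25, so power = 0.40.

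*False positives.* The true rate is assumed to be 30% in both arms.

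- Capture 60% v 40%, 0.30 × 0.60 = 0.18 v 0.30 × 0.40 = 0.12: s0 = 0.0583, s1 = 0.0581. (0.06 − 0.1143)/0.0581 = −0.93. The two tails sum to 0.175 + 0.001, about 0.18.
- Capture 55% v 45%, 0.30 × 0.55 = 0.165 v 0.30 × 0.45 = 0.135: s0 = 0.0583, s1 = 0.0583. (0.03 − 0.1143)/0.0583 = −1.45. The two tails sum to 0.074 + 0.007, about 0.08.

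Summing the two binomial distributions exactly, with the uncorrected chi-squared test applied to each possible table, gives 0.77, 0.41, 0.18 and 0.08. With Fisher's exact test, which Section 5 also allows, the two false-positive figures fall to about 0.12 and 0.05.

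**3. Peak expiratory flow**

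No arithmetic applies. The listed outcome is an expiratory flow, while the scheduled manoeuvre gives an inspiratory volume, in hospital only and without a preoperative value.

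**The case against.** A reader might infer that these outcomes are not measured at all and that the trial cannot answer them. The documents do not support that.

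- **Table 1 is not complete, whatever Section 3.4.1 says.** Adverse events have no row, yet Section 7 schedules them daily in hospital and at all three follow-ups. Absence from the table does not by itself show that an outcome goes uncollected.
- **Routes exist for paresthesia.** Examination, complications and adverse-event recording run to 12 months and could catch some cases. Subjects are blinded, which limits bias in what they report themselves.
- **The appendix 1 forms are not visible.** A paresthesia item or a peak-flow field may be on them.
- **Peak expiratory flow may be only a label.** Incentive spirometry may be what was meant.

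A reader might also infer that nerve injury is what sets the trial apart. Section 1.1 claims novelty for three elements together, and Section 2 says that the objective is met through opioid use and pain scores, both of which are scheduled.

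Finally, the false-positive figure follows the assumed split: 60/40 gives 18%, 55/45 only about 8%, and Fisher's exact test less in each case.

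All of this stands, and it limits the claim to how paresthesia is ascertained and to what Table 1 can yield for peak expiratory flow. It does not remove the gap. None of the visible routes mentions paresthesia, and unblinded staff do the examining and collecting. If the forms do hold the items, Table 1 still has to be brought into line with them.

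**Conclusion.** The point holds in a limited form. Two of 13 secondary outcomes have no specific assessment in a schedule that is said to be complete, and no definition elsewhere in the supplied text. As scheduled, paresthesia incidence is likely to be undercounted and could be ascertained differently by arm. Outcome xi cannot be derived from the incentive spirometry in Table 1.

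The size for paresthesia is illustrative only. Half capture would cut an assumed power of 0.77 to about 0.40, and unequal capture of 55/45 to 60/40 would raise the chi-squared false-positive rate from 5% to about 8% to 18%. No rate or capture fraction in the documents supports any particular value. The primary outcome and the sample size are unaffected. The change should be made because data not recorded at a visit are lost.

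**What to change.** **Paresthesia.** Add a Table 1 row: one yes/no question about the operated side, in identical words for both arms, asked alongside the VAS at baseline, discharge, day 30, 6 months and 12 months. Recording the blinded patient's own answer leaves less to the judgement of unblinded staff. Compare the arms with the chi-squared or Fisher's exact test that Section 5 already plans for proportions, and name the outcome there.

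**Peak expiratory flow.** Either record it at the existing bedside session, or rename outcome xi to the incentive-spirometry volume actually collected. State the time point to be analysed.

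If the appendix 1 forms already collect either item, correct Table 1 to show it.

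**Cost.** One extra question at each of five visits that already take a VAS, and either a peak-flow reading at an existing session or a renamed outcome. No new visit is needed.
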